7.2.4 End of Study Visit

At month 9, subjects will return to the site for the EOS visit for the procedures specified in the Schedule of Assessments ([Table 1](#)).

Subjects who test positive for neutralizing antibodies to romosozumab at the EOS visit or the ET visit will be asked to return for anti-romosozumab antibody testing after EOS for up to 1 year after the last IP administration.

7.3 Description of Study Procedures

The sections below provide a description of the individual study procedures, which are conducted at the timepoints specified in the Schedule of Assessments ([Table 1](#)).

7.3.1 Informed Consent

All subjects must sign and personally date the IRB/IEC-approved informed consent before any study specific procedures are performed.

7.3.2 Demographics

Demographic data collection including sex, age, race, and ethnicity will be collected in order to study their possible association with subject safety and treatment effectiveness. Additionally demographic data may be used to study the impact on BTMs variability and pharmacokinetics of the protocol-required therapies.

7.3.3 Medical History

The investigator or designee will collect a complete medical history starting within 5 years prior to screening through administration of the first dose of IP. In addition, osteoporosis history must date back to the original diagnosis. Medical history will include information on the subject's concurrent medical conditions. All findings are to be recorded on the medical history CRF.

Detailed information will also be collected about the history of hearing disorders and cancer history.

In addition to the medical history above, osteoporosis history must date back to the original diagnosis. Fracture history will be collected from the age of 45 through administration of the first dose of IP. Fracture history will include date of fracture, anatomical site(s) of fracture(s), and degree of trauma involved. Record all findings on the fracture history CRF.

7.3.4 Fracture History

will be collected from the age of 45 through administration of the first dose of IP. Fracture history will include date of fracture, anatomical site(s) of fracture(s), and degree of trauma involved. All findings are to be recorded on the fracture history CRF.

7.3.5 Medication History

The investigator or designee will collect a detailed history of prior therapies affecting bone metabolism that were taken from 5 years prior to screening through randomization. The therapy name, indication, dose, unit, frequency, start date and stop date will be recorded.

A detailed history will also be collected of other prior therapies taken from 30 days prior to study enrollment through randomization. The therapy name, indication, start date and stop date will be recorded.

7.3.6 Substance use History

The investigator or designee will collect information about the prior and/or current use of tobacco and alcohol and substance use. All findings are to be recorded on the CRF.

7.3.7 Physical Examination

A physical examination will be conducted as per standard of care. Physical examination findings should be recorded on the appropriate CRF (eg, medical history, event).

7.3.8 Height and Weight

Body weight should be measured in kilograms without shoes, and height should be measured in centimeters without shoes.

7.3.9 Vital Signs

The following measurements must be performed: systolic/diastolic blood pressure (BP), heart rate, respiratory rate, and temperature. Subject must be in a supine position in a rested and calm state for at least 5 minutes before BP assessments are conducted. If the subject is unable to be in the supine position, the subject should be in most recumbent position possible. The position selected for a subject should be the same throughout the study and documented on the vital sign CRF. The arm with the highest systolic reading at screening will then be used for further BP readings throughout study. The appropriate sized cuff should be used.

The temperature location selected for a subject should be the same that is used throughout the study and documented on the vital signs CRF.

If abnormalities are found and they are considered an adverse event, they are to be recorded on the Event CRF.

7.3.10 Concomitant Medications

Concomitant therapies are to be collected in the CRF from the signing of the ICF through the EOS visit. For concomitant therapies affecting bone metabolism, collect therapy name, indication, dose, unit, frequency, start date, and stop date. For all other concomitant therapies, collect therapy name, indication, start date, and stop date.

7.3.11 Adverse Events, Serious Adverse Events, and Adverse Device Effects

Any serious adverse events occurring after the signing of the ICF through the EOS visit, ET visit, or 30 days after the last dose of IP (whichever period is longer) will be recorded. Any adverse events, adverse device effects, and disease-related events observed by the investigator or reported by the subject occurring after randomization through the EOS visit, ET visit, or 30 days after the last dose of IP (whichever period is longer) will be recorded in the subjects' records and on the appropriate CRFs. Refer to [Section 9.2](#) for more details.

In order to fully evaluate certain events of interest during the study, the following events will be submitted to an independent committee for adjudication:

- potential osteonecrosis of the jaw events
- potential atypical femoral fracture **events**
- **injection site reaction**
- **potential events of serious cardiovascular adverse events**

Further, in order to carefully evaluate cardiovascular events during the trials, all deaths and serious adverse events that are deemed by the investigator to be of potential cardiovascular origin or etiology will be submitted to an independent committee for adjudication, as described in the Clinical Events Classification Charter for Study 20150242. Serious adverse events with terms mapping to a pre-defined preferred term list potentially indicative of cardiovascular etiology will also be adjudicated.

7.3.12 Pharmacokinetic Assessment

Samples for pharmacokinetic assessments will be collected from all subjects enrolled.

Blood samples for pharmacokinetic testing are to be collected at the time points outlined in the Schedule of Assessments ([Table 1](#)). At study visits where pharmacokinetic samples are to be collected and IP is also to be administered, blood samples for pharmacokinetic testing are to be collected prior to administration of IP.

Results from pharmacokinetic assays are considered potentially unblinding and will not be reported to study-related personnel.

7.3.13 Dual-energy X-ray Absorptiometry

Bone density measurements will be performed by DXA. Only Lunar or Hologic bone densitometers will be allowed for the study. The same DXA machine must be used for all study procedures for a particular subject for the duration of the study. All DXA scans will be submitted to and analyzed by the central imaging vendor. A separate procedure manual provided by the central imaging vendor will give specific instructions for acquisition of scans as well as performance of Instrument Quality Control.

Bone density will be measured at the lumbar spine and proximal femur. DXA scans of the lumbar spine will be performed in duplicate (ie, subjects will be removed from the table in between scans). Lumbar spine scans must include L1 through L4. For proximal femur DXA scans, the left side should be used for all scans at all study visits. If the right side must be used (eg, due to implants) or is inadvertently used at baseline, then it must be used consistently throughout the study. If a subject fractures the hip that has been

scanned during the study up to the time of fracture, no further scans will be obtained for the affected location.

All DXA scan data will be submitted electronically to the central imaging vendor for analysis. Sites unable to submit data electronically can submit on compact disc or other media as specified in the DXA Procedural Manual, but electronic submission is preferred.

After analysis by the central imaging vendor, the study site may be asked to re-acquire a scan due to malpositioning or other technical reasons. The study site must comply with the requests from the central imaging vendor. Repeat scans must be performed as soon as possible after the request is received.

7.3.13.1 Screening Bone Mineral Density Assessment

To determine eligibility based on BMD T-score, lumbar spine and proximal femur DXA scans will be analyzed by the central imaging vendor.

For screening purposes, DXA scans of the lumbar spine and proximal femur taken up to 35 days prior to the beginning of the screening period may be used if all of the following criteria are met:

- Images were obtained as part of the routine standard of care, or following appropriate informed consent procedures
- Images were obtained by a trained technician, using the parameters specified by the central imaging vendor for this study (refer to the appropriate imaging manuals provided by the central imaging vendor)
- DXA images were obtained using the same DXA scanner that will be used for this study

To be eligible for the study, subjects must have at least 2 evaluable lumbar vertebrae and at least 1 evaluable proximal femur (as determined by the principal investigator or designee).

7.3.13.2 On-study Bone Mineral Density Assessments

DXA BMD data are considered potentially unblinding. In order to maintain the blind, all DXA scans performed after the screening assessment must not be analyzed by site staff. DXA BMD data obtained after screening will not be reported to study-related personnel, including sites. The results from the central imaging vendor will be used as the final data for statistical analysis.

7.4 Laboratory Assessments

All screening and on-study laboratory samples will be processed and sent to the local and central laboratories, as applicable. Depending on the assessment, the central laboratory will be responsible either for performing the assays, or for shipping samples to Amgen or a specialty laboratory for assay.

The central laboratory will be responsible for all screening and on-study serum chemistry, hematology, hepatitis B and C, serum 25 (OH) vitamin D, and intact-parathyroid (iPTH) tests. The central laboratory will provide a study manual that outlines handling, labeling, and shipping procedures for all serum samples.

Blood samples for BTMs, romosozumab levels, and anti-romosozumab antibodies either will be processed by the central laboratory, sent to an appropriate secondary laboratory or sent to Amgen for analysis or further distribution to other laboratories.

All blood samples will be obtained by venipuncture before IP administration. Blood samples for the assessments of BTMs must be obtained from subjects in fasting state and before noon. Fasting state is defined as overnight fasting. If overnight fasting is not feasible, a minimum 8 hours of fasting is required. The date and time of sample collection will be recorded in the source documents at the site.

Specific analytes for serum chemistry, hematology, and other testing to be conducted on blood and urine samples are shown in [Table 2](#). Although not specifically listed, additional components, abnormal, and/or atypical cells will also be reported if present.

Table 2. Analyte Listing

Serum chemistry	Hematology	BTM	Other analytes
Sodium	Red blood cell	CTX ^a	Romosozumab levels ^a
Potassium	Hemoglobin	P1NP ^a	25 (OH) vitamin D
Chloride	Platelets		iPTH ^a
Bicarbonate	White blood cell		Anti-romosozumab ^a
Total protein	-Differential		antibody
Albumin	-Neutrophils		HepBsAg
Calcium ^a	-Eosinophils		HepBcAb
Albumin-adjusted calcium ^a	-Basophils		Hepatitis C virus
Magnesium	-Lymphocytes		antibody
Phosphorus ^a	-Monocytes		
Glucose			
Blood urea nitrogen			
Creatinine			
TBL			
ALP ^a			
ALT (SGPT)			
AST (SGOT)			
TSH			
Free T4			

ALP = alkaline phosphatase; ALT (SGPT) = alanine aminotransferase (serum glutamic pyruvic transaminase); AST (SGOT) = aspartate aminotransferase (serum glutamic oxaloacetic transaminase); BTM = bone turnover marker; HepBsAg = hepatitis B surface antigen; HepBcAb = total hepatitis B core antibody; iPTH = intact-parathyroid hormone; T4 = thyroxine; TBL = total bilirubin; TSH=thyroid stimulating hormone.

^a Results of post-day 1 assessments will be blinded to any study-related personnel (including the sites) except for serum calcium, albumin-adjusted calcium, phosphorus, or ALP in the event of a panic value.

Results of laboratory assessments for serum calcium, albumin-adjusted calcium, phosphorus, ALP, P1NP, CTX, iPTH, romosozumab levels, and anti-romosozumab antibodies are considered potentially unblinding and will not be reported to any study-related personnel after day 1 in order to maintain the integrity of the study blind. However, in the event of an abnormal value of clinical relevance (panic value) for serum calcium, albumin-adjusted calcium, phosphorus, or ALP, sites will be notified of the unblinded value by the central laboratory. After such notification is issued, the sites may perform additional follow-up blood draws for local analysis as required to support subject medical care. Notifications will also be issued for subjects who test positive for neutralizing anti-romosozumab antibodies at the final scheduled study visit (refer to [Section 7.3](#) for details).

7.5 Antibody Testing Procedures

All subjects will have samples assayed for binding, and if positive, neutralizing antibodies. Blood samples for antibody testing are to be collected at the timepoints indicated in the Schedule of Assessments ([Table 1](#)) for the measurement of anti-romosozumab binding antibodies. Samples testing positive for binding antibodies will also be tested for neutralizing antibodies and may be further characterized for quantity/titer, isotype, affinity and presence of immune complexes. Additional blood samples may be obtained to rule out anti-romosozumab antibodies during the study.

Sites will be notified of any positive neutralizing antibody results to romosozumab detected at the final scheduled visit. If results are not provided, no neutralizing antibodies to romosozumab have been detected at the final scheduled study visit.

Subjects who test positive for neutralizing antibodies to romosozumab at the final scheduled study visit will be asked to return for additional follow-up testing. This testing is to occur approximately every 3 months starting from when the site has been notified of the positive result, until: (1) neutralizing antibodies are no longer detectable or (2) the subject has been followed for a period of at least 1 year (\pm 4 weeks) post administration of romosozumab. All follow-up results, both positive and negative will be communicated to the sites. More frequent testing (eg, QM) or testing for a longer period of time may be requested in the event of safety-related concerns. Follow-up testing is not required where it is established that the subject did not receive romosozumab.

Subjects who test positive for binding, non-neutralizing antibodies and have clinical sequelae that are considered potentially related to an anti-romosozumab antibody response may also be asked to return for additional follow-up testing. Refer to the Schedule of Assessments ([Table 1](#)), as applicable, for specific time points and the laboratory manual for detailed collection and handling instructions.

7.6 Biomarker Development

Biomarkers are objectively measured and evaluated indicators of normal biologic processes, pathogenic processes, or pharmacologic responses to a therapeutic intervention. Biomarker development can be useful in developing markers to identify disease subtypes, guide therapy, and/or predict disease severity. Amgen may attempt to develop test(s) designed to identify subjects most likely to respond positively or negatively to romosozumab.

For all subjects in the study, blood samples will be collected according to the Schedule of Assessments ([Table 1](#)) for determination of BTMs (CTX and P1NP).

7.7 Sample Storage and Destruction

Any blood sample collected according to the Schedule of Assessments ([Table 1](#)) can be analyzed for any of the tests outlined in the protocol and for any tests necessary to minimize risks to study subjects. This includes testing to ensure analytical methods produce reliable and valid data throughout the course of the study. This can also include, but is not limited to, investigation of unexpected results, incurred sample reanalysis, and analyses for method transfer and comparability.

All samples and associated results will be coded prior to being shipped from the site for analysis or storage. Samples will be tracked using a unique identifier that is assigned to the samples for the study. Results are stored in a secure database to ensure confidentiality.

If informed consent is provided by the subject, Amgen can do additional testing on remaining samples (ie, residual and back-up) to investigate and better understand osteoporosis, the dose response and/or prediction of response to romosozumab, characterize antibody response, and characterize aspects of the molecule (eg, mechanism of action/target, metabolites). Results from this analysis are to be documented and maintained, but are not necessarily reported as part of this study. Samples can be retained for up to 20 years.

Since the evaluations are not expected to benefit the subject directly or to alter the treatment course, biomarker development, or other exploratory studies are not placed in the subject's medical record and are not to be made available to the subject, members of the family, the personal physician, or other third parties, except as specified in the informed consent.

The subject retains the right to request that the sample material be destroyed by contacting the investigator. Following the request from the subject, the investigator is to provide the sponsor with the required study and subject number so that any remaining blood samples and any other components from the cells can be located and destroyed. Samples will be destroyed once all protocol-defined procedures are completed. However, information collected from samples prior to the request for destruction, will be retained by Amgen.

The sponsor is the exclusive owner of any data, discoveries, or derivative materials from the sample materials and is responsible for the destruction of the sample(s) at the request of the subject through the investigator, at the end of the storage period, or as appropriate (eg, the scientific rationale for experimentation with a certain sample type no longer justifies keeping the sample). If a commercial product is developed from this research project, the sponsor owns the commercial product. The subject has no commercial rights to such product and has no commercial rights to the data, information, discoveries, or derivative materials gained or produced from the sample.

See [Section 11.3](#) for subject confidentiality.

8. WITHDRAWAL FROM TREATMENT, PROCEDURES, AND STUDY

8.1 Subjects' Decision to Withdraw

Subjects have the right to withdraw from the study at any time and for any reason without prejudice to their future medical care by the physician or at the institution.

Subjects (or a legally acceptable representative) can decline to continue receiving IP and/or other protocol-required therapies or procedures at any time during the study but continue participation in the study. If this occurs, the investigator is to discuss with the subject the appropriate processes for discontinuation from IP or other protocol-required therapies and must discuss with the subject the options for continuation of the Schedule of Assessments ([Table 1](#)) and collection of data, including endpoints and adverse events. The investigator must document the change to the Schedule of Assessments ([Table 1](#)) and the level of follow-up that is agreed to by the subject (eg, in person, by telephone/mail, through family/friends, in correspondence/communication with other physicians, from review of the medical records).

Withdrawal of consent for a study means that the subject does not wish to receive further protocol-required therapies or procedures, and the subject does not wish to or is unable to continue further study participation. Subject data up to withdrawal of consent will be included in the analysis of the study, and where permitted, publically available data can be included after withdrawal of consent. The investigator is to discuss with the subject appropriate procedures for withdrawal from the study.

8.2 Investigator or Sponsor Decision to Withdraw or Terminate Subjects' Participation Prior to Study Completion

The investigator and/or sponsor can decide to withdraw a subject(s) from IP and/or other protocol-required therapies, protocol procedures, or the study as a whole at any time prior to study completion.

Subjects may be eligible for continued treatment with Amgen IP(s) and/or other protocol-required therapies by a separate protocol or as provided for by the local country's regulatory mechanism, based on parameters consistent with [Section 12.1](#).

8.3 Reasons for Removal From Treatment or Study

8.3.1 Reasons for Removal From Treatment

Reasons for removal from protocol-required IP or procedural assessments might include any of the following:

- subject request
- safety concern (eg, due to an adverse event, ineligibility determined, protocol deviation, non-compliance, requirement for alternative therapy, protocol-specified criteria, pregnancy)
- death
- lost to follow-up
- decision by sponsor or investigator (other than subject request, safety concern, lost to follow-up)

In the event a subject experiences a clinical fracture during the study period, the investigator is required to discuss the subject's individual fracture risk and alternative treatment options with the subject and to note the discussion in the subject's records. If a decision is made to begin an alternative approved therapy, the subjects must discontinue IP and every effort should be made to have the subject complete the remaining study visits and assessments, regardless of the alternative therapy chosen by the subject.

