6.7 Excluded Treatments, Medical Devices, and/or Procedures During Study Period

The following treatments are not permitted during the study:

- Strontium (including strontium ranelate and over-the-counter strontium preparations)
- Fluoride (for treatment of osteoporosis)
- Vitamin K and vitamin K analogs (for treatment of osteoporosis)
- Activated vitamin D (1,25-di(OH) vitamin D, or 1 (OH) vitamin D)
- Intravenous bisphosphonates
- Oral bisphosphonates (cumulative dosing regimens of ≤ 1 month are acceptable)
- Denosumab
- Teriparatide or any PTH analogs
- Systemic oral or transdermal estrogen (cumulative dosing regimens of ≤ 1 month are acceptable, vaginal preparations and estrogen creams will be allowed at any time)
- SERMs (cumulative dosing regimens of ≤ 1 month are acceptable)
- Calcitonin (cumulative dosing regimens of ≤ 1 month are acceptable)
- Tibolone
- Prolonged (ie, > 3 months) oral glucocorticoid therapy at a prednisone equivalent dose of ≥ 5.0 mg/day (tapering glucocorticoid courses of ≤ 1 month duration are permitted regardless of dose; inhaled or topical glucocorticoids are permitted)
- Any cathepsin K inhibitor, such as odanacatib (MK-0822):
- Hormonal ablation therapy
- Cinacalcet

If a subject discontinues IP and begins an approved alternative osteoporosis therapy, every effort should be made to have the subject continue participation in the study and complete all scheduled assessments (ie, withdrawal of partial consent, see [Section 8.1](#)).

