12.4 Investigator Responsibilities for Data Collection

The investigator is responsible for complying with the requirements for all assessments and data collection (including subjects not receiving protocol-required therapies) as stipulated in the protocol for each subject in the study. For subjects who withdraw prior to completion of all protocol-required visits and are unable or unwilling to continue the Schedule of Assessments ([Table 1](#)), the investigator can search publically available records (where permitted) to ascertain survival status. This ensures that the data set(s) produced as an outcome of the study is/are as comprehensive as possible.

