9.3.1 BMD by DXA

Missing baseline BMD by DXA at any anatomical site will not be imputed. For purposes of the primary efficacy endpoint analysis and secondary efficacy analyses, observed BMD data at month 6 will be used in the ANCOVA models. **Lumbar spine scans at Month 6 will be acquired in duplicate and the average, when both duplicate values are available, will be used. For proximal femur scans, the left side should be used for all scans at all visits. If the right side must be used or is inadvertently used at baseline, then it must be used consistently throughout the study.** Only BMD values collected from the same body site as the baseline BMD will be used for analyses.

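### Protocol 8.3.1 lets reasons for stopping treatment also end study assessments, so a randomised woman can lose her only post-baseline DXA and leave the primary BMD analysis avoidably

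*Protocol*

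**What the plan says.** **Removal.** The list in Protocol 8.3.1 opens: "Reasons for removal from protocol-required IP or procedural assessments might include any of the following". One of its entries reads "safety concern (eg, due to an adverse event, ineligibility determined, protocol deviation, non-compliance, requirement for alternative therapy, protocol-specified criteria, pregnancy". Protocol 8.2 separately allows the investigator or sponsor to withdraw a woman from product, from procedures or from the study at any time, without listing reasons. Removal from the study has its own list in 8.3.2.

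**Retention.** Three places point the other way.
- The last paragraph of 8.3.1 opens "In the event a subject experiences a clinical fracture during the study period". If alternative therapy is then chosen, product stops, but "every effort should be made to have the subject complete the remaining study visits and assessments, regardless of the alternative therapy chosen by the subject".
- Protocol 6.7 applies whenever a woman stops product and starts an approved alternative osteoporosis therapy, with or without a fracture: "every effort should be made to have the subject continue participation in the study and complete all scheduled assessments".
- Protocol 12.4 makes the investigator responsible for "all assessments and data collection (including subjects not receiving protocol-required therapies".

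**Analysis.** The BMD efficacy set (Protocol 10.1.2, SAP 7.2) needs a baseline scan and at least one post-baseline scan at the site, analysed by randomised group whatever treatment was received. SAP 9.3 imputes nothing unless specified, and SAP 9.3.1 says that "observed BMD data at month 6 will be used in the ANCOVA models". Women who are withdrawn or removed are not replaced (Protocol 3.4).

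**The concern.** Non-compliance, protocol deviation and need for other therapy arise after randomisation and may depend on treatment or on how the woman is doing. Ending product for such reasons need not cost any outcome data. Ending assessments does, because Table 1 schedules DXA after baseline only once, at the Month 6/ET visit. A woman with no scan after baseline cannot be in the BMD efficacy set.

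Both documents promise a comparison of the groups as randomised. Wording that allows the key scan to be dropped together with the treatment works against that promise. It also leaves a site unsure whether 8.3.1 or 6.7 governs. What is at stake is the completeness of the primary endpoint and the meaning of its estimate, not whether the trial can detect a difference from placebo.

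**Working it through.** **Step 1. Compare the passages, reason by reason.**

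| Example in 8.3.1 | Other text | Relation |
|---|---|---|
| Alternative therapy, after a clinical fracture | 8.3.1 last paragraph; 6.7 | Direct conflict if the list is used to end assessments |
| Alternative therapy, no fracture | 6.7 | Direct conflict, as above |
| Ineligibility, deviation, non-compliance | 12.4 | Tension only: 12.4 expects data from women off therapy but does not name these reasons |

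**Step 2. Follow a removed woman to the analysis.**
- *Withdrawn from the study:* Protocol 7.2.3 asks for the Month 6/ET procedures, which include DXA. SAP 13.1.2 assigns any scan from Study Day 2 to Month 6, so she stays in the analysis.
- *Off product, assessments continue:* she has her Month 6 scan and is analysed as randomised.
- *Removed from assessments only:* the 7.2.3 instruction is worded for early withdrawal from the study and does not clearly reach her. With no later scan she is outside the BMD efficacy set, and nothing is imputed.

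Only the third route loses data. The sensitivity analyses in SAP 9.4 and 9.5 deal with outliers and distributional assumptions, not with missing scans.

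**Step 3. Reproduce the plan's power.** Inputs from Protocol 10.2: 30 per arm, difference 6.6, SD 3.9, two-sided 5%, 10% dropout.
- n = 30 × 0.9 = 27 per arm.
- SE = 3.9 × √(2/27) = 1.061; 6.6/1.061 = 6.22; 6.22 − 1.96 = 4.26, giving 99.999% power (normal approximation). The noncentral t gives 99.998%. The stated figure of more than 99% is reproduced.
- By the t calculation, power is 99.9996% with 30 scanned per arm, 99.96% with 21 and 99.4% with 15. The smallest number giving 99% is 14 per arm.

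**Step 4. Illustrate the possible shift.** The documents give no removal rate, so k and r below are assumptions. Let k of 30 romosozumab women be left out, with a fraction r of the effect seen in those kept. Let the placebo arm be complete and the analysed difference be 7.9 (the earlier-study estimate in Protocol 10.2).

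Difference in all randomised = 7.9 × [1 − (k/30)(1 − r)]; overstatement = 7.9 × (k/30)(1 − r).

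| k | r = 0.5: all randomised | overstated by | r = 0: all randomised | overstated by |
|---|---|---|---|---|
| 1 | 7.77 | 0.13 (1.7%) | 7.64 | 0.26 (3.4%) |
| 2 | 7.64 | 0.26 (3.4%) | 7.37 | 0.53 (7.1%) |
| 3 | 7.51 | 0.395 (5.3%) | 7.11 | 0.79 (11.1%) |

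Percentages are relative to the difference in all randomised women. The case k = 3 equals the whole 10% dropout allowance in one arm (3/30).

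**Step 5. Reverse the arm.** If k of 30 placebo women are left out and their mean change is 3.9 points (one SD, assumed) lower than that of the women kept, the analysed placebo mean is too high by (k/30) × 3.9, that is 0.13, 0.26 or 0.39 for k = 1, 2, 3. The treatment difference is then understated by that amount.

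**The case against.** The case against is substantial, and most of it narrows the point.

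- **The list is permissive.** It says what reasons might include, and the four reasons are examples under a safety concern, not free-standing grounds. One list covers two outcomes, and nothing says that every reason applies to both. This stands: exclusion is possible, not prescribed.
- **The protocol leans towards retention.** Besides 6.7 and 12.4, Protocol 7.2 asks that women be kept on schedule, and 8.1 requires that continued assessment be discussed with those who decline product. The ET scan keeps women who leave the study in the analysis. This stands, but none of it clearly covers a woman removed from assessments alone, and a site reading 8.3.1 is not sent to 6.7 or 12.4.
- **The contradiction is limited.** A reader might infer that 8.3.1 contradicts the rest of the protocol on all four reasons. The documents support that for alternative therapy only.
- **It is not an analysis of compliers.** A reader might infer that the primary comparison is confined to women who complied. No analysis set excludes anyone for non-compliance or deviation; SAP 10.3 only summarises and lists deviations. Any woman with a baseline and a post-baseline scan is analysed as randomised.
- **The size is assumed.** The Step 4 figures place all losses in one arm. Even the largest, 0.79, is well inside the planned precision: with 27 per arm the 95% half-width is 2.007 × 1.061 ≈ 2.1 points. This stands. A bias does not disappear because it is smaller than the random error, but this one is modest at most.
- **An early ET scan counted as Month 6** is a matter of the SAP visit window and is not caused by 8.3.1. This stands.

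**Conclusion.** The point holds as a wording defect with a possible, modest effect on the primary estimate. The scope of 8.3.1 reaches assessments although its heading does not. It conflicts with 6.7 on alternative therapy, and with its own last paragraph after a clinical fracture. For ineligibility, deviation and non-compliance it sits badly with 12.4. With a single post-baseline DXA, no imputation and an ET instruction tied to study withdrawal, a woman removed only from assessments can be lost from the primary analysis.

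A reader might go further and infer that the reported effect will be too large. The documents do not support a direction: they give no removal rates or reasons by arm, and Step 5 shows that losses on placebo can push the other way. On-study DXA results are withheld from sites (Protocol 7.3.13.2), so removal cannot follow a known BMD result, although it can follow compliance, tolerability or a fracture. The range of 0.13 to 0.79 points rests wholly on the assumed k and r and on losses in the romosozumab arm alone. Power is not in question, and the test against placebo is very unlikely to change. The change is still worth making, because it prevents avoidable missing primary data at almost no cost.

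**What to change.** 1. In Protocol 8.3.1, delete the reference to procedural assessments from the opening sentence, so that the list governs investigational product only.
2. Add a sentence such as: *Women removed from investigational product for any reason continue all scheduled assessments, including the Month 6 DXA, except on withdrawal of consent, the subject declining the procedure (8.1), death, loss to follow-up, study termination, an assessment that is unsafe, or a scan barred by 7.3.13 because the scanned hip has fractured.* The exceptions are needed so that the sentence does not itself conflict with 8.1 and 7.3.13.
3. Cross-refer 8.3.1 to 6.7 and 12.4.
4. Ask for the Month 6/ET DXA when a woman is removed from assessments under 8.2, not only when she withdraws from the study.

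The authority in 8.2 and 8.3.2, and every rule on stopping product, stay as they are.

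The cost is a short protocol wording change; the visits and scans are already in the schedule. The downside is that data from women off treatment may make the estimated effect slightly smaller.
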